#### 4.9.2 Pharmacokinetics and Pharmacodynamics

PK sampling has only been done up to protocol version 7.0 (inclusive). If PK sampling were initiated in accordance with the previous version of the protocol after Protocol Version 8.0 was approved, collection of PK samples were to continue for the full imlifidase PK profile.

Plasma concentrations of imlifidase will be summarized with number of measurements, number below LLOQ, number of missing data, mean, standard deviation, median, minimum, maximum, geometric mean and CV (%) by time points and presented graphically as mean profiles and by subject profiles. No formal analysis of “outliers” is planned. If the actual time differs more than 20% from the nominal time for a value, that value will not be included in the figure for the mean concentrations.

Plasma concentrations will be presented both as mean plot (both in linear and log-scale) and individual subject plots to show the change over time.

Pharmacokinetics (PK) parameters will be estimated based on measurements of the plasma concentration-time data of imlifidase. The following parameters will be estimated, if possible, but not limited to:

- Maximum serum concentration ( $C_{max}$ )
- Area under the curve (AUC)
- Time to maximum plasma concentration ( $t_{max}$ )
- Terminal half-life ( $t_{1/2}$ )
- Distribution volume ( $V_z$ )
- Volume of distribution, steady state ( $V_{ss}$ )
- Volume of central compartment ( $V$ )
- Clearance (CL) of imlifidase.

PK parameters will be presented with number of measurements, number of missing data, mean, standard deviation, median, minimum, maximum, geometric mean and CV(%). For  $t_{1/2}$ , the harmonic mean will be considered instead of the mean and geometric mean. For  $t_{max}$  only the median, minimum and maximum will be presented.

Plasma concentration values below lower limit of quantification (LLOQ) will be imputed as 0 for descriptive statistics, LLOQ/2 in plots and excluded from PK parameter calculations. Missing values (e.g. no blood sample collected, or no value obtained at analysis) will not be imputed for plasma concentrations descriptive statistics or PK parameter calculations.

In addition, the PK concentrations and PK parameters will be presented in separate listings by subject.

Pharmacodynamics (PD) will be assessed by:

- Effect on IgG following administration of imlifidase
- Effect on identified autoantibodies following administration of imlifidase.
- IgG fragment analysis using SDS-PAGE

The IgG below LLOQ will be imputed using the limit itself for the summary statistics and the plots.

The IgG data will be summarised in tables and presented graphically as mean profiles. Individual data will be plotted over time.

Anti-ganglioside autoantibodies titer data results of Negative will be imputed to 500 for the summary statistics and the plots.

Anti-ganglioside autoantibodies titer data will be summarised in tables and presented graphically over time as mean profiles for each ganglioside antibody and in a mean summary graph with all anti-ganglioside antibodies, if data allows. Individual data will be plotted over time.

IgG and identified autoantibodies will additionally be presented in listings.

SDS-PAGE score data of intact IgG, scIgG and IgG fragments in serum will be presented by subjects and summarised by time point in a table.

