### **1.1.2.3 Pharmacokinetics (PK) and Pharmacodynamics (PD)**

PD and PK will additionally be evaluated as endpoints:

- PK parameters maximum serum concentration ( $C_{max}$ ), area under the curve (AUC), time to maximum plasma concentration ( $t_{max}$ ), terminal half-life ( $t_{1/2}$ ), V, clearance (CL), of imlifidase
- PD effect on IgG following administration of imlifidase
- PD effect on identified autoantibodies regarded as GBS disease specific following administration of imlifidase.

To note, identification of post-infusion antibodies is described in [section 1.1.2.4](#).

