### 3.2 PK/PD analysis set

The PK/PD analysis set (PKPDAS) comprises data from all dosed subjects, with at least one PK or PD data point available post-baseline.

The PK/PD analysis set will be used for presentation of pharmacokinetic and pharmacodynamic endpoints.

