#### 4.1.1 Data presentation

No statistical testing will be performed. Results from analyses will be presented with estimates and 95% confidence intervals (CIs). For log-transformed analyses, the anti-log transformation will be applied before presentation.

No adjustments for multiple testing will be done, since no statistical testing will be performed.

Numerical data will be presented in summary tables by number of subjects, arithmetic mean, median, standard deviation (SD), minimum and maximum. When numerical data are recorded at different time points, absolute values at each time point and changes from baseline may be presented in the summary tables.

Categorical data will be presented by number and percent of subjects as well as number of events (where applicable).

Summaries and analysis of data will in general be presented for all subjects included in the analysis set, unless otherwise specified in the output shell.

All data will be listed by subject and time point (if applicable).

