### 4.9 Other endpoints

#### 4.9.1 Anti-ganglioside antibodies

Biomarker assessment (analysis of anti-ganglioside antibodies and neurofilament light chain levels) will be evaluated as an exploratory endpoint.

Pre-dose samples will be screened for anti-ganglioside antibodies and presented in a table as positive or negative. The anti-ganglioside antibodies data will be listed by subject.

Neurofilament light chain levels will be summarized in a table and presented in a listing by subject. In addition, neurofilament light chain levels will be presented both as mean plot and individual subject plots to show the change over time.

Moreover, a separate plot will show anti-ganglioside antibodies titers per subject over time up to Day 92 (collected as part of Visit 8) together with the swimmer plot of the GBS disability scores and the subgroup MRC scores on FAS.

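### Anti-ganglioside titres: with Negative set to 500 and no baseline-positive restriction or log scale specified, the default mean can understate the fall or follow one high-titre subject

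*SAP*

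**What the plan says.** SAP 4.9.2 gives the substitution rule: "Anti-ganglioside autoantibodies titer data results of Negative will be imputed to 500 for the summary statistics and the plots". The titre data are then summarised in tables and "presented graphically over time as mean profiles for each ganglioside antibody and in a mean summary graph with all anti-ganglioside antibodies", the pooled graph only if the data allow. The section does not state who enters these summaries or on what scale the mean is taken.

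The general rules therefore apply:

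- SAP 4.1.1, on tables: "Numerical data will be presented in summary tables by number of subjects, arithmetic mean, median, standard deviation (SD), minimum and maximum".
- SAP 4.1.1, on the denominator: "Summaries and analysis of data will in general be presented for all subjects included in the analysis set, unless otherwise specified in the output shell".
- SAP 3.2, on the PK/PD set, which "comprises data from all dosed subjects, with at least one PK or PD data point available post-baseline". Antibody status is not a condition of membership.

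The endpoint in SAP 1.1.2.3 is narrower: "PD effect on identified autoantibodies regarded as GBS disease specific following administration of imlifidase". SAP 4.9.1 already plans a baseline classification: "Pre-dose samples will be screened for anti-ganglioside antibodies and presented in a table as positive or negative". Nothing links that classification to the titre summaries.

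For imlifidase concentrations, SAP 4.9.2 asks for a geometric mean, CV% and mean plots on both linear and log scales. It asks for none of these for titres. SAP 4.1.1 does provide for back-transformation of log-scale analyses, but no section assigns titres to such an analysis.

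**The concern.** A subject who is negative for an antibody before dosing has no titre to lose. Under the default rules that subject still contributes 500 at every visit while Negative, which pulls the mean change towards zero.

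The second problem is separate. Titres are read on a multiplicative scale, so an arithmetic mean gives most of its weight to the highest values. One subject can decide whether the profile appears to fall.

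At stake is how readable the summary table and mean figure are for a listed pharmacodynamic endpoint (Protocol 2.2; SAP 1.1.2.3). Because the study does no hypothesis testing, such summaries are the form in which the result is reported.

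**Working it through.** The plan gives no titre effect, positivity rate or derivation of 500, so there is no figure of its own to reproduce.

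**Inputs from the documents.** N = 30 (the approximate target, SAP 2.2); Negative = 500 (SAP 4.9.2); arithmetic mean and median over the analysis set (SAP 4.1.1, 3.2).

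**Assumptions.** k subjects are positive for a given antibody, all at baseline titre T. Never-positive subjects stay at 500. Full clearance means that every positive subject becomes Negative.

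**Formulas**

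- Mean over all at baseline = [kT + (N − k) × 500] / N; after full clearance it is 500.
- Mean absolute change over all = (k/N) × mean change in positives.
- Geometric mean ratio over all = (ratio in positives)^(k/N).

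**Step 1: dilution at a moderate titre (T = 4,000).** In positives the fall is (4,000 − 500)/4,000 = 87.5%, a change of −3,500.

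| k | Mean, before to after | Fall in mean | Mean change | Median, before to after |
|---|---|---|---|---|
| 3 | 850 to 500 | 41.2% | −350 | 500 to 500 |
| 9 | 1,550 to 500 | 67.7% | −1,050 | 500 to 500 |
| 15 | 2,250 to 500 | 77.8% | −1,750 | 2,250 to 500 |

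For k = 3: (3 × 4,000 + 27 × 500)/30 = 25,500/30 = 850, and 350/850 = 41.2%. If fewer than half the subjects are positive, the all-subject median is 500 at both times, so the planned median shows no fall.

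**Step 2: dilution at a high titre (T = 64,000, k = 9).** The baseline mean is (576,000 + 10,500)/30 = 19,550. The fall is 19,050/19,550 = 97.4%, against 63,500/64,000 = 99.2% in positives. The percentage is hardly diluted. The mean absolute change is still scaled by 9/30: −19,050 against −63,500.

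**Step 3: one high-titre subject, positives only.** Take five positives at 1,000, 1,000, 2,000, 4,000 and 64,000. The first four clear and the last does not change.

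- Arithmetic mean: 72,000/5 = 14,400 to 66,000/5 = 13,200, a fall of 8.3%.
- Geometric mean: the individual ratios are 1/2, 1/2, 1/4, 1/8 and 1, with product 1/128. Its fifth root is 0.379, a fall of 62.1%.
- Adding 25 never-positive subjects at 500 changes the arithmetic fall only to 6,000/84,500 = 7.1%. This example therefore shows the effect of the averaging scale, not of dilution.

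The distortion can run the other way. With one subject at 64,000 and eight at 2,000, where only the first clears, the arithmetic mean in positives falls 79.4% (8,889 to 1,833). The geometric mean falls 41.7% and the median does not move.

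**Step 4: does either change suffice alone?** No. Step 3 shows that restricting to positives leaves the one-subject problem. Taking the geometric mean over all 30 leaves the dilution: for T = 4,000 and k = 9 the ratio is (1/8)^(9/30) = 0.536, a fall of 46.4% against 87.5% in positives.

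**Step 5: the substitute value.** With nine positives at 2,000, all becoming Negative, the all-subject mean falls 92.1% if Negative is set to 50, 67.7% at 250, 47.4% at 500 and 23.1% at 1,000. In positives only, the falls are 97.5%, 87.5%, 75.0% and 50.0%. The documents do not relate 500 to the lowest titre that the assay can report.

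**The case against.** **The denominator is a default, not a statement.** A reader might infer that the SAP takes mean titres over all subjects. SAP 4.9.2 does not say so. The all-subject rule in SAP 4.1.1 is general and yields to the output shells, which are not in the documents. The wording about identified autoantibodies, with pre-dose screening, could also mean that only positives are titrated. In that case 500 would serve mainly for positives who turn Negative. This stands: the dilution is conditional on the default. It does not remove Step 3. A subject positive for one antibody may also be negative for another, and unless handled per antibody would enter that other profile at 500.

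**The arithmetic mean is specified for tables only.** SAP 4.1.1 names it for summary tables, whereas SAP 4.9.2 speaks only of mean profiles for the figures. This also stands, although no other mean is named for titres.

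**The size rests on assumed titres and rates.** True. At high titres the percentage dilution almost vanishes. The percentage falls above are what a reader would take from a mean profile; the SAP does not plan percentage change for titres.

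**A large effect would not be hidden.** The plan also has individual titre plots, listings, the pre-dose positivity table and a per-subject plot to Day 92 with disability and MRC sub-scores (SAP 4.9.1, 4.9.2). With about 30 subjects, a fall in the positives can be seen there. This limits the consequence but does not repair the summary itself.

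**The mechanism does not hang on this display.** A reader might infer that it does. The documents do not support that: total IgG and SDS-PAGE fragment analysis are also planned as pharmacodynamic measures, and anti-ganglioside analysis is also labelled exploratory (Protocol 2.2.1; SAP 1.1.2.4).

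**Conclusion.** The point holds as a minor to moderate one about a descriptive pharmacodynamic display. Followed as written, with the default rules, the SAP produces a weak summary of a listed endpoint for two separate reasons.

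- **Dilution** applies if the output shells keep the all-subject default. Mean absolute change is scaled by k/N whatever the titre. The percentage fall is materially diluted only at low to moderate titres.
- **Dominance by one subject** applies to any arithmetic mean of titres, whichever subjects are included.

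The direction of both follows from arithmetic. The size rests on the assumed N = 30, positivity counts and titres. No test, decision rule or efficacy result is affected.

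**What to change.** In SAP 4.9.2, for each ganglioside antibody:

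1. Summarise titres in subjects positive for that antibody before dosing, and show n. If the SAP 4.9.1 table does not record positivity per antibody, take it from the pre-dose titre result.
2. Report geometric mean titre, geometric mean fold change from baseline, and n/N that have become Negative at each visit. Draw the mean profiles on the log scale.
3. Use 500 only for a positive subject who turns Negative. State how 500 relates to the assay's lowest reportable titre, and show the result under one alternative value.
4. List separately any subject who is first positive after dosing, since the restriction would otherwise drop that subject.
5. Drop the pooled all-antibody mean graph, or show it on the log scale.

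Items 1 and 2 need to be made together, as Step 4 shows.

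The SAP change log records version 2.0 as updated during the main analysis. If that analysis is complete, add these as a documented supplementary output in the clinical study report or its Day 360 addendum, beside the planned tables.

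The cost is SAP wording, a subset flag and a few outputs; no new data are needed. The drawback is that numbers per antibody will be visibly small and the geometric means imprecise, so the individual plots should stay.

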#### **4.9.3      Pregnancy test**

Serum  $\beta$ -hCG will be determined for all female subjects at screening and on Day 180 (visit 9). All pregnancy test results will be presented in a listing by subject.

#### **4.9.4      Nerve conduction study (NCS)**

Nerve conduction study (NCS) might be measured at Days 15 and 29. NCS is performed using standard techniques at least on one side of the body.

The NCS assessments details will be included only in the SDTM datasets (ie will not be presented in the TFLs).

#### **4.9.5      SARS-CoV-2 virus PCR-test**

At the screening visit an evaluation of the result of the SARS-CoV-2 virus PCR-test, performed at hospital admission or later, will be done.

SARS-CoV-2 virus PCR-test assessments details will be presented in a listing by subject.

## 5 Interim analyses

No interim analyses are planned.

The main analyses for the CSR will be based on all data up to and including visit 9 (Day 180). To note, at time of the main analysis some subjects will have also the visit 10 (Day 360) performed, ie will have completed the study. All data available at time of database lock will be included in the main analyses, meaning that some subjects will have completed the study.

Remaining data from visit 10 (Day 360) will be included in an addendum to the CSR.

## 6 Deviations from protocol analysis

The following changes have been considered in current SAP as compared to study protocol:

- Minor wording on the FAS definition as compared to protocol. Change has been made in order to make the definition clearer.
- Percentage change from baseline summaries will be not presented for the vital signs and laboratory assessment results (ie clinical chemistry, haematology and urinalysis).
- The main analyses for the CSR will be based on all data included in the database at time of database lock, including visit 10 (Day 360) data for subjects that reached that stage (ie completed the study).

## 7 Quality control

ADaM data sets will be based on the SDTM data sets. The programming of the ADaM datasets will be performed in SAS and QC of the programs will include

- Independent code review
- QC of SDTM input data vs output in ADaM or listings

Tables, listings and figures (TLF) will be created by SAS programs and based on the ADaM data sets. To note, if only listings are planned to be presented on a particular data (ie no tables and figures) then that can be created using the SDTM data sets.

The programming of TLFs will be reviewed by an independent person.

SAS Viya version 3.5 or later, will be used for data handling and presentation.

## 8 Layout of output

The output will follow [REDACTED] standard output templates. Tables, figures and listings will be prepared as individual RTF (Rich text format) files. Separate Word documents will be created for tables (called 14.x), figures (called 14.x), and listings (called 16.x) respectively.

Margins and font will be chosen to respect the requirements for filing with EMA (European medicines agency) and FDA (the US Food and drug administration).

In the page header of each table/listing, a table/listing number followed by the title of the table/listing will be presented. After the title line, optional sub-title or population information can be presented. Footnotes will be put in the footer at the bottom of the page.

SAS program name, name of output file, location of files and date of creation of each table/listing/figure will appear below the output. Page number will appear on the top right corner and sponsor name and status (draft/final) on the top left of the header of each page for each table/listing/figure.

In a listing, in the case that a subject's record has been continued to the next page, an appropriate identification (e.g., the subject ID number) must be presented at the beginning of that page.

## 9.2 Appendix 2 - Centile metric score calculated for the R-ODS

The following nomogram allows the translation of raw sum scores of the final R-ODS (range 0 to 48) to logits or to a centile metric score with values ranging from 0 (most severe activity and social participation restrictions) to 100 (no activity and social participation limitations). Rasch analysis calculates the corresponding logits and centile metric.

R-ODS summed raw score	Rasch person location (logits)	centile metric
0	-6.95	0
1	-6.03	6
2	-5.36	11
3	-4.87	14
4	-4.48	16
5	-4.14	19
6	-3.84	21
7	-3.57	22
8	-3.32	24
9	-3.09	26
10	-2.87	27
11	-2.66	28
12	-2.46	30
13	-2.26	31
14	-2.07	32
15	-1.88	34
16	-1.70	35
17	-1.52	36
18	-1.33	37
19	-1.15	39
20	-0.97	40
21	-0.79	41
22	-0.61	42
23	-0.42	43
24	-0.24	45
25	-0.05	46
26	0.14	47
27	0.34	48
28	0.53	50
29	0.73	51
30	0.94	52
31	1.15	54
32	1.36	55
33	1.58	57
34	1.81	58
35	2.04	60
36	2.28	61
37	2.54	63

38	2.80	65
39	3.09	67
40	3.40	69
41	3.74	71
42	4.11	73
43	4.54	76
44	5.03	80
45	5.59	83
46	6.25	88
47	7.07	93
48	8.11	100

### 9.3 Appendix 3 - Vital Sign Parameters Normal Ranges

All vital signs measurement results below/above the normal range will be flagged as Low (L)/High (H) results, as per criteria defined below:

Vital Sign Parameter	Lower range	Upper range
Systolic Blood Pressure (mmHg)	less than 120	140 or higher
Diastolic Blood Pressure (mmHg)	less than 80	90 or higher
Oxygen Saturation (%)	less than 95	NA
Pulse Rate (beats/min)	less than 60	100 or higher
Respiratory Rate (breaths/min)	less than 12	20 or higher
Body Temperature (C)	less than 36.4	37.8 or higher

## 10 Change log

Version	Effective date	Reason for revision
1.0	14-SEP-2023	Finalized as v1.0.
2.0	21-FEB-2024	Finalized as v2.0 (updated during main analysis).
